5.2 Dose Limiting Toxicity

Toxicities will be graded according to CTCAE version 4.0 of the NCI Common Terminology Criteria for Adverse Events CTCAE version 4.0 is identified and located on the CTEP website at http://ctep.cancer.gov/protocolDevelopment/electronic_applications/ctc.htm.

All appropriate treatment areas should have access to a copy of CTCAE version 4.0. Management and dose modifications associated with adverse events are outlined in Section 6.

DLT will be defined as any of the events listed in this section that are at least possibly related to the investigational agent that occur during the dose-finding period regardless of expectedness. Management and dose modifications for toxicities which occur outside of the dose-finding period should also follow section 6; however these will not be considered dose limiting for the purpose of dose escalation.

Patients who come off therapy for reasons other than toxicity before completing the dose-finding period may be replaced for purposes of estimating the MTD, as discussed in section 13.1.

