5.2.1 The following are Dose-Limiting Toxicities (DLT's)

- A PD-0332991 (IBRANCE) related adverse event will be considered dose-limiting if it leads to a dose reduction or permanent cessation of treatment during the first course of therapy. All dose modifications in all courses are to follow the guidelines provided in section 6.2.

- Inability to receive the next cycle of PD-0332991 (IBRANCE) within two weeks of the last dose because of lack of hematologic recovery or persisting non-hematologic toxicity.

5.2.1.1 Non-hematologic dose limiting toxicity is defined as:

- Any grade 4 non-hematologic toxicity
- Any grade 3 non-hematologic toxicity with the exception of:
 - Grade 3 nausea and vomiting of < 5 days
 - Grade 3 diarrhea and/or electrolyte disturbances which have not been maximally treated
 - Grade 3 AST/ALT elevation that returns to levels meeting eligibility criteria within 7 days of study drug interruption and does not recur upon restarting drug.
- Any Grade 2 non-hematologic toxicity that persists for > 7 days and is considered medically significant or sufficiently intolerable by patients requires treatment interruption.

5.2.1.2 Hematologic dose limiting toxicity is defined as:

- Grade 3 neutropenia with fever and sepsis
- Any Grade 4 hematologic toxicity with the exception of lymphopenia
- Grade 3 thrombocytopenia and/or requiring a platelet transfusion on 2 separate days within a 7-day period

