5.4.6 Febrile neutropenia

Febrile neutropenia should be managed according to the local institutional guidelines. Measures include laboratory testing, blood and urine cultures, and institution of broad spectrum antibiotics.

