5.5.2 Off Treatment Criteria

At the discontinuation of treatment, the “Off Treatment Date” is to be recorded in the eCRF and is to be consistent with the reason given for going off treatment. The “Last Treatment Date” is defined as the last date that the patient received protocol based therapy. Date of “off treatment” must be the greatest of the date of last treatment, date of procedure, date of patient assessment, notification of patient/family decision, or decision made by the physician that resulted in the patient being taken off protocol treatment. The reason for discontinuation of treatment must be documented by the attending investigator in the medical record and recorded in the eCRF.

Patients will be considered Off Treatment for the following reasons:

- Development of unacceptable toxicity as outlined in section [5.2.1](#). See section [7](#) for specific reporting requirements.
- Progressive disease (PD) as described in section [11.1.4](#).
- Development of a medical or psychiatric illness that in the investigator's judgment renders the patient incapable of further therapy on this protocol or the treating physician determines continuation on this study is not in the patient's best interest.
- Interruption greater than 14 days of continued drug administration for reasons unrelated to toxicity
- The patient, parent or legal guardian refuses further treatment on this protocol.
- Completion of all protocol defined treatment
- Pregnancy
- Non Compliance that in the opinion of the investigator does not allow for ongoing participation.
- Termination of the study by the sponsor
- Investigational Agent/Device manufacturer can no longer provide the study agent.

Patients who are off protocol therapy must be followed until an Off Study Criterion is met.

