6.2 Hematologic and Non-Hematologic Adverse Events and Management

Table 8

Event	AE Grade or Observation	Dose Modification
Diarrhea or other non-hematologic toxicity	Grade 1 or 2	Maintain dose; continue anti-diarrheal treatment.
	Grade 3 (non-dose limiting)	Hold PD-0332991 (IBRANCE) and maximally treat. If toxicity resolves to meet on study parameters within 14 days of drug discontinuation or (as outlined in Section 5.2.1.1), restart treatment at the same dose.
	Grade 3 or 4 (dose limiting)	Hold PD-0332991 (IBRANCE) and maximally treat. If toxicity resolves to meet on study parameters with 14 days of drug discontinuation, restart treatment at next lower dose level if patient at dose level 2 or 3 and meets BSA requirements for the next lower dose level. If patient at dose level 1 or with BSAs smaller than what is required should come off treatment permanently. If toxicity does not resolve to meet study eligibility parameters within 14 days of drug discontinuation, the patient must be removed from protocol therapy. If dose limiting toxicity recurs in a patient who has resumed treatment at the reduced dose level, the patient must be removed from protocol therapy.
Hematologic	Grade 1 or 2	Maintain dose.
	Grade 3 (non-dose limiting)	Maintain dose.
	Grade 3 or 4 (dose limiting)	Hold PD-0332991 (IBRANCE). Counts should be checked at least twice weekly (3-4 days apart) during this time. If toxicity resolves to meet on study parameters with 14 days of drug discontinuation, restart treatment at next lower dose level, if patient is at dose level 2 or 3 and meets BSA requirements for the next lower dose level. If patient at dose level 1 or with BSAs smaller than what is required should come off treatment permanently. If toxicity does not resolve to meet study eligibility parameters within 14 days of drug discontinuation, the patient must be removed from protocol therapy. If dose limiting toxicity recurs in a patient who has resumed treatment at the reduced dose level, the patient must be removed from protocol therapy.

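### Table 8 tells sites to maintain the dose for Grade 3 neutropenia with fever but no sepsis; add an explicit hold and leave the DLT list unchanged

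*Combined protocol and SAP*

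**What the plan says.** - **DLT list (5.2.1.2).** There are three hematologic entries. The only one that mentions fever is "Grade 3 neutropenia with fever and sepsis". The others are Grade 4 events other than lymphopenia, and Grade 3 thrombocytopenia and/or repeated platelet transfusion.
- **General DLT rule (5.2.1).** A drug-"related adverse event will be considered dose-limiting if it leads to a dose reduction or permanent cessation of treatment" in the first course. Failure to start the next cycle in time through lack of recovery also counts.
- **Table 8 (6.2), hematologic.** The row that begins "Grade 3 (non-dose limiting" carries the action to maintain the dose.
- **Table 8 (6.2), non-hematologic.** The row with the same label says "Hold PD-0332991 (IBRANCE) and maximally treat", then restart at the same dose on recovery.
- **Table 8, dose-limiting events with no lower level.** "If patient at dose level 1 or with BSAs smaller than what is required should come off treatment permanently".
- **Supportive care (5.4.6).** "Febrile neutropenia should be managed according to the local institutional guidelines". The measures named are laboratory tests, cultures and antibiotics. Holding study drug is not among them.
- **Scope (5.2).** "Management and dose modifications for toxicities which occur outside of the dose-finding period should also follow section 6", so Table 8 governs every course.

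**The concern.** Myelosuppression is the drug's main dose-limiting toxicity. The Schema says that heavily pretreated patients, the group now enrolling in Stratum II, are likely to have hematologic toxicity. For a febrile child with a Grade 3 neutrophil count and no sepsis, the only explicit dosing instruction is to carry on at the same dose. It applies for up to 26 courses. Sites that hold drug on local practice and sites that follow Table 8 literally would manage the same event differently.

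**Working it through.** The plan gives no figure on this point to reproduce, so most of the check sets the sections side by side.

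**Step 1. Where the event lands.** Take drug-related Grade 3 neutropenia with fever and without sepsis. It fails the febrile entry in 5.2.1.2 (no sepsis), the Grade 4 entry (Grade 3 count) and the platelet entry. It could be argued to be non-hematologic. However, 5.2.1.2 treats neutropenia with fever as hematologic, and the CAEPR (7.1) files febrile neutropenia under blood and lymphatic disorders. It therefore goes to the hematologic non-dose-limiting Grade 3 row.

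**Step 2. Which other rules make it a DLT.**

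| Circumstance in the dose-finding period | DLT? |
|---|---|
| Dose reduction or permanent stop in course 1 | Yes (5.2.1, first bullet) |
| Next cycle delayed beyond two weeks from last dose, no recovery | Yes (5.2.1, second bullet) |
| Count reaches Grade 4 | Yes (5.2.1.2) |
| Related Grade 3 or higher non-hematologic event, such as infection, outside the listed exceptions | Yes (5.2.1.1) |
| Related Grade 2 non-hematologic event for more than 7 days, medically significant or intolerable, needing interruption | Yes (5.2.1.1) |
| Short febrile episode, Grade 3 count, timely recovery, no reduction | No |

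Only the last row is the gap. A temporary hold alone does not make the event a DLT.

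**Step 3. Compare the two non-dose-limiting Grade 3 rows.** The non-hematologic row holds, treats, and restarts at the same dose if the event resolves within 14 days. The hematologic row maintains. Because the table uses a hold where it wants one, maintaining most naturally reads as not holding. The Study Calendar (section 10, note A) steps up blood counts only at Grade 4 neutropenia or thrombocytopenia, so it adds no monitoring here.

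**Step 4. Does a hold with a 14-day limit fit the existing DLT rules?** If the hold starts by day 14, the limit is reached by day 14 + 14 = 28, inside course 1, and removal is a permanent cessation under the first bullet of 5.2.1. If it starts on days 15 to 21, the limit falls on days 29 to 35. The delayed-cycle bullet, which covers both hematologic and non-hematologic non-recovery, then applies, and 5.1.1 extends the dose-finding period when the next course is delayed. No new DLT rule is needed.

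**Step 5. Can an effect on escalation be claimed?** The one documented frequency is the CAEPR column of under 3% for all febrile neutropenia among 1,751 patients. It is not specific to children, Stratum II, course 1 or non-septic cases. As an illustration only, assume a rate p for all other DLTs and q for this event, mutually exclusive, with r = p + q. If the event were counted, the chance of at most 1 DLT in 6 would be (1−r)⁶ + 6r(1−r)⁵:

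| p | q = 0 | q = 1% | q = 2% | q = 3% |
|---|---|---|---|---|
| 5% | 96.7% | 95.4% | 93.9% | 92.3% |
| 10% | 88.6% | 86.6% | 84.4% | 82.2% |
| 20% | 65.5% | 63.1% | 60.6% | 58.2% |

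The fall is 1.3 to 7.3 percentage points. Under 13.2 one counted event in six still allows escalation. Both p and q are assumptions, so the table bounds a hypothesis and is not a finding about this trial.

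**The case against.** **The plan does not forbid a hold.** Maintaining the dose can be read as no change of dose level. Section 5.4.6 defers to local guidelines, and its list of measures need not be exhaustive. Section 5.5.2 lets the treating physician stop treatment in the patient's interest. This stands in part: an investigator can act, and it would be too strong to say that every such child must keep taking drug. But no section states the hold, and Table 8's contrast between its two Grade 3 rows points the other way.

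**The remaining event is narrow.** This stands, as Step 2 shows.

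**A reader might infer that the event should be a DLT, or that the Stratum I MTD is in doubt.** The documents do not support either. What limits dose is a design choice, and the Stratum I MTD was set under the current list. No such event is reported, and no applicable rate is given. Listing it would also do harm if nothing else changed. Table 8 would permanently remove any affected child at 50 mg/m², and any at 75 mg/m² with BSA from 0.93 to 1.19, who falls below the 1.20 limit for level 1. Section 5.5.2 separately makes "Development of unacceptable toxicity as outlined in section" 5.2.1 a reason to leave treatment. A same-dose restart for a newly listed DLT at level 1 would sit awkwardly beside permanent removal for Grade 4 neutropenia at that level.

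**Conclusion.** The gap holds as a minor safety point. For a short febrile episode with a related Grade 3 neutrophil count, no sepsis and timely recovery, Table 8 says to maintain the dose and no other section says to hold. This rests on reading the event as hematologic and on Table 8 meaning what its contrasting rows suggest. How often the event occurs in these children cannot be told from the documents. No bias in escalation and no error in the Stratum I MTD is claimed.

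**What to change.** Add one line to the hematologic part of Table 8, for all courses, and cross-reference it from 5.4.6:

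> *Grade 3 neutropenia with fever (non-dose limiting): hold PD-0332991, check counts at least twice weekly, and restart at the same dose once afebrile with ANC at least 1,000/mm³ within 14 days; if not recovered within 14 days, remove from protocol therapy.*

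The ANC threshold is the one in 3.2.10. The twice-weekly counts and the 14-day limit are those Table 8 already uses for dose-limiting hematologic events. The protocol sets no temperature for fever, so the line relies on the local definition. Leave 5.2.1.2, the Rolling-6 rules and the Stratum I MTD unchanged. Because the event stays off the DLT list, 5.5.2 needs no edit and no recount is required. The Stratum II maximum stays at 2 × 6 + 6 = 18.

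**Cost.** A few missed doses per event and an occasional removal for non-recovery. In course 1, 20 doses are planned (21 minus the Day 2 dose held for pharmacokinetics), so missing four or more leaves fewer than the 17 in 13.1.1. That makes a patient inevaluable only if he or she also leaves treatment for a reason other than toxicity during the dose-finding period. Existing non-hematologic holds carry the same risk. A hold might also prevent some Grade 4 counts. The documents do not allow that to be quantified.

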5.3 Criteria for starting subsequent courses

A course may be repeated every 28 days if the patient has at least stable disease and has again met laboratory parameters as defined in Section [3.2.10](#). The labs can be performed within 48 hours prior to the start of each course. If a patient does not meet these parameters at the end of the treatment course (at day 28), then PD-0332991 (IBRANCE) can be held for up to 7 days until parameters meet the eligibility criteria. Drug can be held for up to 14 days in patients who undergo surgical procedures for reasons other than tumor progression to allow for proper wound healing.

5.4 Concomitant Medications and Supportive Care Guidelines

5.4.1 Steroids

Corticosteroids should be used at the lowest dose to control symptoms of edema and mass effect, and discontinued, if possible. Use of corticosteroids should be recorded in the Rave database.

5.4.2 Anticonvulsants

Only non-enzyme inducing anticonvulsants drugs should be used, if indicated. Use of such anticonvulsants should be recorded in the Rave database.

5.4.3 Growth Factors

Routine use of growth factors (i.e. G-CSF, GM-CSF, and erythropoietin) is not permitted. However, therapeutic use of G-CSF in patients with serious neutropenic conditions, such as sepsis, may be used at the investigator's discretion. Use of such growth factors should be recorded in the Rave database.

5.4.4 Anti-emetics

The use of anti-emetics will be at the investigator's discretion (see [Appendix B](#) for contraindicated medications). Use of anti-emetics should be recorded in the Rave database.

5.4.5 Proton Pump Inhibitors

The use of proton pump inhibitors (PPI) (e.g. rabeprazole, omeprazole, pantoprazole, lansoprazole or esomeprazole) is not permitted due to a significant decreased exposure to PD-0332991 (IBRANCE) when concurrently given. If a patient is already receiving a PPI, treatment should be discontinued and a wash-out period of at least 24 hours should have elapsed before beginning therapy with PD-0332991 (IBRANCE). However, alternative antacid therapies may be used including H₂-receptor antagonists, and locally acting antacids. H₂-receptor antagonists should be administered with twice daily dosing regimen. PD-0332991 (IBRANCE) should be given at least 10 hours after H₂-receptor antagonist evening dose and 2 hours before the H₂-receptor antagonist morning dose. Local antacid should be given at least 2 hours before or after PD-0332991 (IBRANCE) administration.

5.4.6 Febrile neutropenia

Febrile neutropenia should be managed according to the local institutional guidelines. Measures include laboratory testing, blood and urine cultures, and institution of broad spectrum antibiotics.

5.4.7 Pneumocystis jiroveci pneumonia (PJP) prophylaxis

The use of medication (i.e., Bactrim) for PJP prophylaxis in patients on chronic steroids is recommended, but is at the investigator's discretion.

5.4.8 Neurosurgical Procedures

If a neurosurgical procedure is required for a reason other than tumor progression (i.e. the onset of hydrocephalus), these procedures should be documented, but will not constitute criteria for declaring the patient "off therapy". Due to the possible effect of myelosuppression on wound healing, PD-0332991 (IBRANCE) should be held for at least 7 days or until the patient has clinically recovered from the effects of surgery and has demonstrable wound healing before resuming treatment. Treatment can be held for up to 14 days.

5.4.9 Concomitant Therapy

Other anti-cancer or experimental agents are not permitted. Drugs that are known to interact with the investigational agent are not allowed during the trial and are listed in [Appendix B](#),

[Appendix C](#) and Section [8.1.1.11](#).

5.5 Duration of Therapy

In the absence of treatment delays due to adverse event(s) or disease progression, treatment may continue for 26 courses (approximately two years) or until one of the Off Treatment Criteria applies as noted in [5.5.2](#).

5.5.1 On Study Data Submission Schedule

Pre-treatment, on-study and off-treatment data, as well as patient response data are to be recorded in the electronic data collection screens using the Rave database. See the Required Data and Timetable for Submission form located on the PBTC-042 Protocol webpage for the schedule. For assistance, contact the PBTC Protocol Coordinator listed on the cover page. An optional roadmap is located on the PBTC-042 Protocol Webpage.

5.5.2 Off Treatment Criteria

At the discontinuation of treatment, the “Off Treatment Date” is to be recorded in the eCRF and is to be consistent with the reason given for going off treatment. The “Last Treatment Date” is defined as the last date that the patient received protocol based therapy. Date of “off treatment” must be the greatest of the date of last treatment, date of procedure, date of patient assessment, notification of patient/family decision, or decision made by the physician that resulted in the patient being taken off protocol treatment. The reason for discontinuation of treatment must be documented by the attending investigator in the medical record and recorded in the eCRF.

Patients will be considered Off Treatment for the following reasons:

- Development of unacceptable toxicity as outlined in section [5.2.1](#). See section [7](#) for specific reporting requirements.
- Progressive disease (PD) as described in section [11.1.4](#).
- Development of a medical or psychiatric illness that in the investigator's judgment renders the patient incapable of further therapy on this protocol or the treating physician determines continuation on this study is not in the patient's best interest.
- Interruption greater than 14 days of continued drug administration for reasons unrelated to toxicity
- The patient, parent or legal guardian refuses further treatment on this protocol.
- Completion of all protocol defined treatment
- Pregnancy
- Non Compliance that in the opinion of the investigator does not allow for ongoing participation.
- Termination of the study by the sponsor
- Investigational Agent/Device manufacturer can no longer provide the study agent.

Patients who are off protocol therapy must be followed until an Off Study Criterion is met.

5.5.3 Data Submission Schedule for Patients Off Treatment

Subjects will be monitored for the resolution (or return to baseline) of all toxicities considered at least possible related to PD-0332991 (IBRANCE) occurring while on treatment and/or within 30 days after the last administration of study drug. Toxicities that are ongoing at the end of day 30 of last treatment date will be followed until resolution or return to baseline or until the patient is

off study.

5.5.4 Criteria for Removal from Study (Off Study Criteria)

The date and reason for the patient coming off study must be documented in the eCRF and the Operations, Biostatistics and Data Management Core must be notified according to standard reporting guidelines (see sections [7](#), [12](#)).

- Patient determined to be ineligible.
- Parent, patient, or guardian withdraws consent for continued participation.
- Patient death while on study. The IRB, Investigational Drug Branch (IDB), Study Chair and OBDMC must be notified as per section [7](#).
- Initiation of another anti-cancer therapy
- Patient has been observed for the resolution of all toxicities occurring while on treatment and for 30 days following the last administration of study drug.
 - If the patient was found to be ineligible after starting treatment, the 30 day follow-up would still be necessary unless the patient commences a different anti-cancer therapy.

5.5.5 Data Submission for Patients Off-Study

No data will be collected documenting treatment or reporting events or disease status that occur subsequent to the official “off study” date with the exception of adverse events with an attribution of possible, probable, or definite that occur after the “off study” date for the study drug. (see section [7](#)).

6 DOSING DELAYS/ DOSE MODIFICATION

6.1 Notification of Study Chair

The study chair or co-chair must be notified of any dosage modifications, prior to the implementation of the dose modification

6.2 Hematologic and Non-Hematologic Adverse Events and Management

Table 8

Event	AE Grade or Observation	Dose Modification
Diarrhea or other non-hematologic toxicity	Grade 1 or 2	Maintain dose; continue anti-diarrheal treatment.
	Grade 3 (non-dose limiting)	Hold PD-0332991 (IBRANCE) and maximally treat. If toxicity resolves to meet on study parameters within 14 days of drug discontinuation or (as outlined in Section 5.2.1.1), restart treatment at the same dose.
	Grade 3 or 4 (dose limiting)	Hold PD-0332991 (IBRANCE) and maximally treat. If toxicity resolves to meet on study parameters with 14 days of drug discontinuation, restart treatment at next lower dose level if patient at dose level 2 or 3 and meets BSA requirements for the next lower dose level. If patient at dose level 1 or with BSAs smaller than what is required should come off treatment permanently. If toxicity does not resolve to meet study eligibility parameters within 14 days of drug discontinuation, the patient must be removed from protocol therapy. If dose limiting toxicity recurs in a patient who has resumed treatment at the reduced dose level, the patient must be removed from protocol therapy.
Hematologic	Grade 1 or 2	Maintain dose.
	Grade 3 (non-dose limiting)	Maintain dose.
	Grade 3 or 4 (dose limiting)	Hold PD-0332991 (IBRANCE). Counts should be checked at least twice weekly (3-4 days apart) during this time. If toxicity resolves to meet on study parameters with 14 days of drug discontinuation, restart treatment at next lower dose level, if patient is at dose level 2 or 3 and meets BSA requirements for the next lower dose level. If patient at dose level 1 or with BSAs smaller than what is required should come off treatment permanently. If toxicity does not resolve to meet study eligibility parameters within 14 days of drug discontinuation, the patient must be removed from protocol therapy. If dose limiting toxicity recurs in a patient who has resumed treatment at the reduced dose level, the patient must be removed from protocol therapy.

